The protocol, informed consent form(s), recruitment materials, and all participant materials will be submitted to the Institutional Review Board (IRB) for review and approval. Approval of both the protocol and the consent form must be obtained before any participant is enrolled. Any amendment to the protocol will require review and approval by the IRB before the changes are implemented to the study. In addition, all changes to the consent form will be IRB-approved; a determination will be made regarding whether a new consent needs to be obtained from participants who provided consent, using a previously approved consent form.

[figure not shown]
1 Protocol Summary

1.1 Synopsis

Title:	A Randomized, Double-Blind, Controlled Study to Assess the Efficacy and Safety of Intravenous Phenobarbital in Neonatal Seizures
Study Description:	
This is a multicenter, randomized, double-blinded, active-controlled, parallel study in neonates (≥ 34 - ≤ 44 gestational weeks).
 
This study is designed to evaluate the efficacy, safety and tolerability of intravenous phenobarbital in treatment of neonatal seizures diagnosed by continuous video EEG (cvEEG).
 
This study will consist of a Screening Period, Treatment Period, Follow-up Period and Open Label Extension Period.

Objectives:	
Primary Objective: The primary objective is to evaluate a potential dose-response of two different doses of intravenous phenobarbital for safety and efficacy in a neonatal population at high risk for seizures.
 
Secondary Objectives:
 
 • To assess the safety and tolerability of intravenous phenobarbital administration in neonates experiencing seizures. • To assess the requirement of a second dose of intravenous phenobarbital in neonates with ongoing seizures. • To assess the requirement of alternative anticonvulsive therapy in neonates with ongoing seizures after the second dose of intravenous phenobarbital. • To characterize the seizure burden following administration of intravenous phenobarbital.
Endpoints	
Primary Endpoint:
 
 • Percent of neonates who do not require additional seizure treatment after the first dose of phenobarbital during the first 24 hours after treatment. 
Secondary Endpoints:
 
 • Percent of neonates who do not require additional seizure treatment for 2 hours after the first dose of phenobarbital. • Percent of neonates who do not require additional seizure treatment after the second dose of phenobarbital within the first 24 hours of treatment.

	
 Seizure burden over 24 hours following initial administration of the phenobarbital injection. Seizure burden over 48 hours following initial administration of the phenobarbital injection. Percent of neonates requiring alternative anticonvulsive therapy for the management of seizures at 24 and 48 hours Time period between the first dose and second dose of intravenous phenobarbital in neonates randomized. Time period between the second dose of intravenous phenobarbital to alternative anticonvulsant treatment in neonates randomized. Time period between the first dose of intravenous phenobarbital to administration of an alternative anticonvulsant treatment in neonates randomized.
Study Participant Population	Male or female neonates with a gestational age of ≥ 34 - ≤ 44 weeks admitted into the NICU with a high probability of developing seizures
Phase:	Phase III
Description of Sites/Facilities Enrolling Participants	Level III/IV NICU
Description of Study Drug	
Phenobarbital 20 mg/kg (first/initial dose) followed by 20 mg/kg (if required)
 
Phenobarbital 40 mg/kg (first/initial dose) followed by 10 mg/kg (if required)
 
The doses will be administered intravenously over a 30-minute period.

Study Duration:	
Estimated Study Start Date: Q4 2020
 
Estimated Primary Completion Date: Q3 2023
 
Estimated Study Completion Date: Q4 2023

Participant Duration:	Total study duration for a single neonate is up to 5 days.

1.2 Schema

Protocol
MI-5780Version: 2.0; 07-Dec-2021
Phenobarbital Sodium Injection

1.3 Schedule of Events

Study Procedure	Screening Period	Double-Blind Treatment Period	Follow-Up Period / Early Discontinuation/ End of Study
Study Day(s)	-1-0	0-1	1-2
NICU Admission	X		
Informed Consent	X		
Inclusion/Exclusion Criteria	X		
Delivery History	X		
Medical History	X		
Apgar Score	X		
Physical Examination (includes neurological exam)	X ¹		X ²
Height/Length (include Head Circumference and Abdominal Circumference)	X		
Body Weight	X		
Vital Signs ^{1,3}	X	X	X
Laboratory Safety Tests (Hematology, Chemistry, Coagulation) ^{1,4}	X	X	X
Continuous Video EEG Assessment ⁵	X	X	X
Clinical Seizure Assessment ⁶		X	X
Randomization		X	
Phenobarbital Administration		X	
Phenobarbital Maintenance Administration		X	X
Phenobarbital PK Samples ⁷		X	X
Recording of Additional Anticonvulsant Medication		X	
Prior and Concomitant Medication Review	X	X	X
Adverse Events Evaluation	X	X	X

Protocol
MI-5780

Version: 2.0; 07-Dec-2021

Phenobarbital Sodium Injection

Page 16 of 76

1. All neonates will undergo a baseline physical exam (including a neurologic exam), baseline vital signs (blood pressure, pulse rate, respiration rate, oxygen saturation, and auxiliary or rectal temperature) and baseline laboratory safety tests.
2. Physical examination and neurologic exam to be completed at end of Follow-up Period and/or prior to discharge.
3. Vital signs will be monitored and recorded prior to each (loading dose and second dose) phenobarbital treatment administration and every 15 ± 5 minutes up to 1 hour after the completion of each 30-minute dose infusion. Recording of vital signs will continue to be collected every 4-6 hours post phenobarbital administration through the Treatment Period and until completion of the Follow-up Period or at early study discontinuation. The 4-6 hours is calculated from initial loading dose start of infusion time.
4. Laboratory safety tests will be collected at the completion of the Treatment Period, at end of Follow-up Period and every 24 hours during the Open-Label Extension Period or at time of discharge/early study discontinuation.
5. cvEEG monitoring will be recorded for the study from time of informed consent or start of cvEEG (which ever comes last) and up to 48 hours after first loading dose of phenobarbital.
6. Clinical seizure assessment will be monitored and recorded prior to each phenobarbital treatment dose and at 30 and 60 minutes after the completion of each 30-minute dose infusion. At the end of Treatment and Follow-up Period, whether seizures were observed clinically will be documented in the eCRFs.
7. Collection of plasma samples for phenobarbital analysis will be obtained:
 - o PK Group 1: 30 minutes, 4-6 hours post initial dose,
 - o PK Group 2: 30 minutes, 10-12 hours post initial dose,
 - o PK Group 3: 30 minutes, 16-18 hours post initial dose,
 - o PK Group 4: 30 minutes, 22-24 hours post initial dose,
 - o A sample will be collected after second dose infusion is complete (if applicable)
 - o A sample will be collected at end of Follow-up Period or at time of discharge/discontinuation.
 - o During the Open Label Extension Period, phenobarbital plasma concentrations will be obtained every 24 hours post initial dose up to 120 hours and or at time of discharge/discontinuation.

Protocol
MI-5780Version: 2.0; 07-Dec-2021
Phenobarbital Sodium Injection

Confidential

Page 17 of 76

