6.5 Concomitant Therapy

6.5.1 Allowed Concomitant Medication

For this protocol, a prescription medication is defined as a medication that can be prescribed only by a properly authorized/licensed clinician. Medications to be reported in the Case Report Form (CRF) are concomitant prescription medications, over-the-counter medications (if applicable) and supplements (if applicable).

Only the short acting benzodiazepine lorazepam and midazolam administered ≥ 8 hours before enrollment will be permitted prior to study entry.

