8.2.2 Pregnancy and Delivery History

Current delivery information will be recorded for the following:

- Date of delivery
- Delivery presentation

- Occiput posterior
- Occiput anterior
- Brow
- Face
- Compound
- Transverse
- Breech
- Other (please specify)
- Unknown

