9.4.2 Analysis of the Primary Efficacy Endpoint(s)

The primary endpoint will be summarized by number and percent of participants with events and compared by a log binomial model (a generalized linear model [GLM]) that includes treatment as a study variable, which will generate risk ratio (RR) together with their 95% CIs of having a primary outcome between high dose and low dose groups. A study participant who is withdrawn from the study within the first 24 hours after treatment will be considered not to have achieved the primary endpoint. Treatment of such dropouts with respect to other endpoints will be specified in the SAP.

In addition, covariate adjustment will be performed by GLM model with treatment as a study variable and, gender, gestational age, birth weight, apgar scores, liver function tests, seizure etiology, therapeutic hypothermia and pre-treatment seizure burden as covariates. From this

model, adjusted RR together with their 95% confidence interval will be derived. Imputation for these baseline missing covariates will be carried out for adjusted analysis.

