9.4.7 Subgroup Analyses

Subgroup analysis for the primary outcome will be performed in a series of predefined strata, which will include gender, gestational age, birth weight, Apgar scores, liver function tests, seizure etiology, therapeutic hypothermia, pre-informed consent seizure burden and pre-treatment seizure burden. Assessment of the homogeneity of treatment effect by a subgroup variable will be conducted by a GLM with the treatment, subgroup variable, and their interaction term as predictors, and the *P*-value presented for the interaction term.

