5.3. Planned Covariates

Covariate analyses will be performed on the primary outcome on the ITT population. The prespecified covariates in this study will be:

Stratification factors

- Presence or absence of HIE
- High or low seizure burden

Baseline values

- Gender (binary)
- Gestational age (continuous)
- birth weight (continuous)
- Apgar scores (continuous)
- Liver function tests (Total Protein, Albumin, Bilirubin, ALP, AST, ALT) (continuous)
- Seizure etiology (binary)
- pre-treatment seizure burden (continuous)

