5.4. Subgroup

Subgroup analysis for primary outcome on the ITT population will be performed in a series of predefined strata, which was defined as below. Imputation for these baseline missing covariates will be carried out before categorizing.

Grouping Variable	Subgroups
Gender	Male or Female

CONFIDENTIAL

Birth weight	Dichotomised at median
Apgar scores	Dichotomised at median
Liver function tests (Total Protein, Albumin, Bilirubin, ALP, AST, ALT)	Dichotomised at median
Seizure etiology	Yes or No
Therapeutic hypothermia	Yes or No
Pre-treatment seizure burden	Dichotomised at median

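### Neither document names a data source for therapeutic hypothermia or birth weight, both of which are planned covariates or subgroups, and the SAP would fill gaps with random draws before forming subgroups

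*Protocol*

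**What the plan says.** **Planned uses.** Protocol 9.4.2 describes an adjusted model with gender, "gestational age, birth weight, apgar scores, liver function tests, seizure etiology, therapeutic hypothermia and pre-treatment seizure burden as covariates". Protocol 9.4.7 has birth weight among its subgroups, and its list ends with "seizure etiology, therapeutic hypothermia, pre-informed consent seizure burden and pre-treatment seizure burden". SAP 5.3 lists birth weight as a continuous covariate but does not list hypothermia. SAP 5.4 lists both as subgroups, with birth weight split at the median and hypothermia as yes or no. Protocol 3.2.3.1 names cooling as a covariate to explore in the PK work.

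**Planned collection.** Footnote 1 of the Schedule of Events (protocol 1.3) says "All neonates will undergo a baseline physical exam (including a neurologic exam), baseline vital signs", followed by the individual vital signs, including temperature, and the laboratory tests. The same schedule and the screening list in 4.1.2 have a body weight item. Section 8.2.2 says "Current delivery information will be recorded for the following", and then gives only date of delivery and presentation. Section 8.2.1 covers relevant conditions, family history of seizures and delivery complications. Section 6.5.1 says "Medications to be reported in the Case Report Form (CRF) are concomitant prescription medications", plus over-the-counter products and supplements.

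**Missing values.** SAP 5.5.1 imputes a missing baseline covariate by random draws whose mean and SD, or category probabilities, come from the available sample. SAP 5.4 adds: "Imputation for these baseline missing covariates will be carried out before categorizing".

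**The concern.** Sex, gestational age, Apgar scores and liver tests each have a named source in the protocol. Therapeutic hypothermia and birth weight do not. A site that follows the written lists exactly would not record cooling status, because cooling is not a medication and is not among the listed assessments.

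The protocol gives its own reasons to care about both variables. Section 2.2.1 says that clearance rises with birth weight and may be reduced under cooling, and 2.3.1.2 says that cooling may raise serum concentrations. In a comparison of two loading doses these are reasonable candidates for effect modification.

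If cooling status were captured for only part of the sample, the SAP's random draws would mix cooled and uncooled neonates in both subgroups and pull their treatment effects together. A reader would then see a smaller subgroup difference than the data could have shown.

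**Working it through.** **1. The plan's own figure.** With 50% against 70%, two-sided alpha 0.05, 80% power and pooled variance: n = [1.960·√(2·0.6·0.4) + 0.842·√(0.25 + 0.21)]² / 0.20² = (1.358 + 0.571)² / 0.04 ≈ 93 per arm, 186 in total. Then 186/0.95 = 195.8, so 196. The stated figures reproduce, and nothing in this point changes them.

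**2. Search for a source.**

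| Place | Cooling | Birth weight |
|---|---|---|
| Protocol 1.3, rows and footnotes | not named; temperature recorded | not named; body weight at screening |
| Protocol 4.1.2, screening list | not named | not named; body weight listed |
| Protocol 8.2.1, medical history | not named | not named |
| Protocol 8.2.2, delivery history | not named | not named |
| Protocol 6.5.1, CRF medication rule | medications and supplements only | not applicable |
| Protocol 8.3.5, adverse event record | concomitant procedures, within an event record only | not applicable |

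No rule derives cooling status from temperature, and none says that screening body weight stands in for birth weight.

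**3. Effect of the imputation rule on the hypothermia subgroup.** Let p be the true prevalence of cooling. Let f be the fraction with known status, with missingness unrelated to true status. The rest are drawn with probability p.

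- True prevalence among those recorded as cooled: f + (1 − f)p.
- True prevalence among those recorded as uncooled: (1 − f)p.
- The difference is f, whatever p is. The difference in treatment effect between recorded subgroups is therefore f times the true one, on the risk-difference scale.

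The documents give none of the inputs. As an assumed illustration take p = 0.5, low-dose response 50% in both groups, and risk differences of 0.30 uncooled and 0.10 cooled:

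| f | RD, recorded uncooled | RD, recorded cooled | Difference |
|---|---|---|---|
| 1 | 0.300 | 0.100 | 0.20 |
| 0.75 | 0.275 | 0.125 | 0.15 |
| 0.50 | 0.250 | 0.150 | 0.10 |
| 0.25 | 0.225 | 0.175 | 0.05 |

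A simulation of 400,000 neonates gave 0.201, 0.147, 0.102 and 0.047, in agreement. SAP 7.1.4 uses risk ratios for subgroups. At f = 0.50 these are 0.75/0.50 = 1.50 and 0.65/0.50 = 1.30. The log of their ratio is ln(1.30/1.50) = −0.143, against ln(1.20/1.60) = −0.288 with full capture, so the shrinkage is again about one half.

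**4. Random draws against observed values only.** Take the same assumptions, 196 neonates and 49 per cell.

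- Full capture: SE = √[(0.25 + 0.16 + 0.25 + 0.24)/49] = 0.136. Power ≈ Φ(0.20/0.136 − 1.96) ≈ 31%.
- f = 0.50 with random draws: SE = √[(0.25 + 0.1875 + 0.25 + 0.2275)/49] = 0.137. Power ≈ Φ(0.10/0.137 − 1.96) ≈ 11%, and the estimate is halved.
- f = 0.50 with observed values only, 24.5 per cell: SE = √(0.90/24.5) = 0.192. Power ≈ Φ(0.20/0.192 − 1.96) ≈ 18%, and the estimate keeps its full size.

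**5. Birth weight.** If a share m of values is drawn at random from a normal distribution, the correlation with the true value falls to about 1 − m, and about m/2 of neonates land on the wrong side of a median split. For assumed m of 10%, 25% and 50%, the correlation is 0.90, 0.75 and 0.50, and the misplaced share is 5%, 12.5% and 25%.

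**The case against.** The strongest reply is that absence from a protocol list is not absence from the CRF. Protocol 10.1.10.1 and 10.1.11 refer to an eCRF, worksheets and manuals that are not supplied. This stands. A reader might infer that the analyses cannot be run, or that they would rest wholly on invented values. The documents do not support either reading. Either item may be captured in the eCRF, and if a variable were never collected the imputation rule would have no sample to draw from. The dilution applies to partial capture only.

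Other parts of the reply also stand:

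- Screening body weight covers most of the birth-weight half, which reduces it largely to saying which weight is meant.
- A reader might infer that cooling begun after the first dose would count as a baseline subgroup. The SAP calls these variables baseline, and for vital signs and laboratory tests it defines baseline as the last value before dosing (8.2, 8.3). That argues against the inference, although no time point is written for hypothermia itself.
- The documents do not support calling cooling the likeliest effect modifier. They say only that it may alter exposure. With the half-life of 114 ± 43 hours in protocol 8.2.7.1, elimination over 24 hours is 1 − 2^(−24/114) ≈ 14%, or about 21% at 71 hours, so slower clearance has limited room to act within the endpoint window.
- With about 31% power under the assumptions above, a null interaction would say little even with complete data.
- SAP 5.6 treats additional primary-outcome analyses as exploratory, and SAP 7.1.4 cautions against over-reading subgroups.

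The reply does not remove the missing source for cooling status. It also leaves in place an imputation rule that shrinks the comparison when data are partial, and the mismatch between protocol 9.4.2 and SAP 5.3.

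**Conclusion.** The point holds in limited form. Neither document names a source for therapeutic hypothermia or birth weight. For birth weight a close substitute is collected; for cooling there is at best a proxy. Where cooling status is partly missing, the SAP's rule reduces the subgroup difference to about f of its true size. That result assumes missingness unrelated to true status; the range of 0.25 to 0.75 for f is an assumption.

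The analyses affected are the covariate-adjusted analysis, the subgroup analyses and the exploratory PK work. Hypothermia enters the adjusted analysis only through the protocol, because SAP 5.3 omits it. The SAP primary model adjusts for HIE and seizure burden only, so the primary test, the 196 randomized, alpha and power are unaffected. The change is worth making because it is cheap and replaces a written rule that dilutes the comparison.

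**What to change.** 1. In protocol 1.3, 4.1.2 and 8.2, add a chart-abstracted baseline item: therapeutic hypothermia in progress at T0, yes or no, with start and stop times. If the eCRF already has it, cite it there.
2. In SAP 5.4, define the hypothermia subgroup as status at T0 and analyse observed values only, without random imputation.
3. Either record birth weight from the chart, or state in SAP 5.3 and 5.4 that screening body weight is used instead.
4. Reconcile the covariate list in protocol 9.4.2, which includes hypothermia, with SAP 5.3, which does not.

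The cost is a few CRF fields and short edits to both documents, with no new procedure and no change in sample size. Protocol 8.2.4 already accepts retrospective Apgar scores, so chart abstraction has a precedent. The one downside is that a neonate with unknown cooling status drops out of that subgroup analysis.

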1.3.1 Schedule of Events (Open Label Extension Period)

Study Procedure	Open Label Extension Study Day(s)	Open Label Discharge/End of Open Label 2-4
NICU Admission		
Informed Consent		
Inclusion/Exclusion Criteria		
Delivery History		
Medical History		
Apgar Score		
Physical Examination (includes neurological exam)		X ¹
Height/Length (include Head Circumference and Abdominal Circumference)		
Body Weight	X	
Vital Signs	X ²	X ²
Laboratory Safety Tests (Hematology, Chemistry, Coagulation)	X ³	X ³
Continuous Video EEG Assessment ⁴		
Clinical Seizure Assessment	X ⁵	X ⁵
Randomization		
Phenobarbital Administration	X	
Phenobarbital Maintenance Administration	X	
Phenobarbital PK Samples ⁶	X	X
Recording of Additional Anticonvulsant Medication	X	X
Prior and Concomitant Medication Review		X
Adverse Events Evaluation	X	X

1. Physical examination and neurologic exam to be completed prior to discharge.
2. Vital signs will be monitored and recorded prior to each phenobarbital maintenance treatment administration and every 15±5 minutes up to 1 hour after the completion of each 30-minute dose infusion. Recording of vital signs will continue to be collected

Protocol
MI-5780

Version: 2.0; 07-Dec-2021
Phenobarbital Sodium Injection

Confidential

Page 18 of 76

every 4-6 hours hour post phenobarbital administration until the completion of the Open Label Extension Period or at study discharge. The 4-6 hours is calculated from initial loading dose start of infusion time.

3. Laboratory safety tests will continue to be collected every 24 hours during Open-Label Extension Period or at time of discharge/early study discontinuation.
4. cvEEG monitoring will be recorded from time of informed consent or start of cvEEG (which ever comes last) and up to 48 hours and up to 48 hours after first loading dose of phenobarbital. If study participant enters Open Label Extension before end of Follow-up Period, cvEEG recording and monitoring will continue until the 48 hours is complete. cvEEG recording and monitoring after 48 hours is not required per this protocol and will follow site's standard of practice.
5. Clinical seizure assessment will be recorded prior to each phenobarbital maintenance treatment administration and at 30- and 60-minutes after the completion of each 30-minute dose infusion. At the end of each 24-hour Open Label Maintenance Study, whether seizures were observed clinically will be documented in the eCRFs.
6. Collection of plasma samples for phenobarbital analysis will be obtained every 24 hours post initial loading dose up to 120 hours and or at time of discharge/discontinuation.

2 Introduction

2.1 Study Rationale

This is a randomized, double-blind, parallel-group, phase 3 study to evaluate the efficacy of the administration of phenobarbital sodium injection in neonates who have suffered from electrographic or electroclinical seizure. As neonatal seizures can have long-term adverse effects, including death, placebo-controlled studies are not appropriate for this population. This study is designed to show intravenous phenobarbital is effective at preventing subsequent seizures by demonstrating greater efficacy at a higher dose compared to a lower dose.

2.2 Background

Phenobarbital is one of the first barbiturates synthesized and is one of the approximate 50 barbiturates used clinically. Phenobarbital has an extensive history with nearly 100 years of use as a sedative, hypnotic and anticonvulsant drug. It is recommended by the World Health Organization (WHO) as a first-line agent for partial and generalized tonic-clonic seizures in developing countries.

Currently, phenobarbital is one of the oldest and most utilized antiepileptic drugs worldwide. The drug is relatively safe, and provides a cost-effective alternative to other antiseizure medications (ASMs), making this drug a more popular choice. Despite other conventional ASMs including carbamazepine, sodium valproate and phenytoin replacing phenobarbital as a first-line agent and possible behavior and cognitive side effects as well as sedation from drug use, phenobarbital continues to be a second- or third-line agent in the developed world.

Phenobarbital is commonly administered orally in tablet form for prophylactic purposes but can also be used parenterally when the oral route is impossible or impractical (i.e. emergency situations). Phenobarbital is administered parenterally as a slow intravenous (IV) injection or given as an intramuscular (IM) injection. Subcutaneous routes are not recommended.

Phenobarbital sodium injection is no longer a first-line therapy for many types of acute epileptic seizures since it has been largely replaced by newer parenteral antiepileptic drugs such as lorazepam, “which is the most commonly administered benzodiazepine for status epilepticus when intravenous access is available”⁽¹⁾. Other intravenous antiepileptic drugs available in the USA include phenytoin, fosphenytoin, levetiracetam, sodium valproate, and lacosamide.

However, phenobarbital remains the first-line therapy for acute seizures in neonates in the USA and international survey data indicate that it remains the most commonly used agent in this setting ⁽²⁾. Seizures occur more often during the newborn period (2-3.5 per 1000 live births) than at any later age. Neonatal seizures can lead to frequent and serious long-term consequences in survivors, such as later epilepsy and significant cognitive and motor disabilities. A National Hospital Discharge Survey indicates that the incidence of all types of neonatal seizures is 2.84 per 1,000 live births in the United States; similar rates of neonatal seizures have been reported in population-based studies in California (0.95/1000 live births) and Texas (1.8/1000 live births) ⁽³⁻⁵⁾. For

hypoxic-ischemic encephalopathy specifically, similar incidence rates of 1-3 per 1000 live births have been reported in the United States and other high-income countries (6, 7). In a recent Task Force Report for the ILAE Commission of Pediatrics, phenobarbital, carbamazepine, and valproate were recommended choices for benign infantile convulsions, but the committee indicated that each was “possibly effective” and that the published data were “weak” with overall recommendations of “C” (possibly effective, ineffective, or harmful, or as useful/predictive or not useful/predictive) for all three drugs according to the American Academy of Neurology (AAN) grading system (8).

